7.3.2 Demographics and Baseline Characteristics

The following baseline characteristics will be summarized by treatment group, for the population of All Treated Subjects as well as the population of All Subjects Treated in Part 2. All baseline presentations will identify subjects with missing measurements. Listings will also be provided.

- Age (descriptive statistics)
- Age category I (< 65, ≥ 65)
- Age category II (< 65, ≥ 65- < 75, ≥ 75)
- Gender (male, female)
- Race (white, black, asian, other)
- Region (US, EU, Australia, Rest of World)
- Baseline ECOG Performance Status (0, 1)
- M Stage at Study Entry (M0, M1a, M1b, M1c) (source: CRF)
- AJCC Stage at Study Entry (III, IV)
- Weight (descriptive statistics)
- PD-L1 Status (≥5%, <5%/indeterminate) (source: clinical database)
- BRAF mutation status (BRAF mutant, wildtype) (source: CRF)
- BRAF mutation test (Cobas+THxID, Other, Unknown)
- Baseline LDH (≤ ULN, > ULN)
- Baseline LDH (≤ 2*ULN, > 2*ULN)
- History of Brain Metastases (Yes, No)

- Smoking Status (Yes, No)
 - Time from Initial Disease Diagnosis to Randomization (< 1 year, 1-< 2 year, 2-< 3 year, 3-< 4 year, 4-< 5 year, ≥ 5 year)
 - All lesions (Investigator Tumor Assessments at Baseline): sites of disease, number of disease sites per subject.
 - Target lesions (Investigator Tumor Assessments at Baseline): Presence of target lesions, site of target lesion, sum of longest diameter of target lesion.
- Similarly the following IVRS data will be summarized for Arms A and B by treatment group as randomized.
- M Stage at Study Entry (M0/M1a/M1b/M1c)
 - PD-L1 Expression Level (≥5% and <5%/indeterminate)

7.3.3 Medical History

General medical history will be listed by subject.

7.3.4 Prior Therapy

The following will be summarized by treatment group for All Treated Subjects.

- Prior neo-adjuvant therapy (yes/no)
- Prior adjuvant therapy (yes/no)
- Time from completion of prior adjuvant therapy (< 6 months and ≥ 6 months) for subjects who received prior adjuvant therapy
 - For subjects in Arms A and B time will be measured to randomization.
 - For subjects in Cohort C time will be measured to first dose of study therapy.
- Prior surgery related to cancer (yes/no)
- Prior radiotherapy (yes/no)

Agents and medication will be reported using the generic name. A listing by subject will also be provided.

7.3.5 Baseline Examinations

Subjects with abnormal baseline physical exam results will be tabulated by examination criteria (eg, neck, cardiovascular, lungs, etc) and by treatment group for All Treated Subjects.

7.3.6 Discrepancies between IVRS and CRF information

Summary tables (cross-tabulations) of stratification factors for All Treated Subjects in Arms A and B by treatment group will be provided to show any discrepancies between what was reported through IVRS vs. CRF data or clinical database (baseline).

- M Stage at Study Entry (IVRS vs. CRF data)
- PD-L1 status (IVRS vs. clinical database)

7.4 Extent of Exposure

Analyses will be performed by treatment group “as treated” in all treated subjects, unless otherwise specified.

7.4.1 Administration of Study Therapy

Arms A and B:

The following parameters will be summarized (descriptive statistics) by treatment group:

- Time from randomization to first dose of study therapy (0 to 3 days, > 3 to 7, > 7 to 14, > 14 to 21, > 21 to 28, > 28)
- Number of concomitant doses received (nivolumab + ipilimumab) and number of nivolumab flat doses received. A subject will be considered to have received concomitant doses of nivolumab and ipilimumab if both infusions are administered on the same date. This summary will be repeated for the subset of subjects in Arm A or Arm B who experienced a drug-related Grade 3-5 AE, as specified in the primary endpoint definition (Section 4.1).

The following parameters will be summarized (descriptive statistics) by treatment group and study therapy (nivolumab and ipilimumab). during Part 1 for All Treated Subjects:

- Number of doses received
- Cumulative dose in mg/kg
- Relative dose intensity (%) using the following categories: < 50%; 50 - < 70%; 70 - < 90%; 90 - < 110%; ≥ 110%
- Infusion duration in minutes

This summary will be repeated for the subset of subjects in Arm A or Arm B who experienced a drug-related Grade 3-5 AE, as specified in the primary endpoint definition (Section 4.1).

In addition, the following parameters will be summarized (descriptive statistics) by treatment group for nivolumab flat dosing during Part 2 for All Subjects Treated in Part 2:

- Number of doses received
- Cumulative dose in mg
- Relative dose intensity (%) using the following categories: < 50%; 50 - < 70%; 70 - < 90%; 90 - < 110%; ≥ 110%.

- Infusion duration in minutes.

This summary will be repeated for the subset of subjects in Arm A or Arm B who experienced a drug-related Grade 3-5 AE, as specified in the primary endpoint definition (Section 4.1).

Cohort C:

The following parameters will be summarized (descriptive statistics):

- Number of concomitant doses received (nivolumab + ipilimumab) and number of nivolumab flat doses received. A subject will be considered to have received concomitant doses of nivolumab and ipilimumab if both infusions are administered on the same date.

The following parameters will be summarized (descriptive statistics) by study therapy (nivolumab and ipilimumab)

- Number of doses received
- Relative dose intensity (%) using the following categories: < 50%; 50 - < 70%; 70 - < 90%; 90 - < 110%; ≥ 110%.
- Infusion duration in minutes.

For Arm A, Arm B, and Cohort C duration of treatment will be presented by treatment group using a Kaplan-Meier curve whereby the last dose date will be the event date for those subjects who are off study therapy. Median duration of treatment and associated 95% CI will be provided. Subjects who are still on study therapy will be censored on their last dose date. Duration of study therapy will also be summarized in a table with descriptive statistics (mean, minimum, and maximum). The percentage of subjects with study therapy duration > 3 months, > 6 months, > 9 months, and > 12 months will be tabulated. This table will be repeated for the subset of subjects in Arm A or Arm B who experienced a drug-related Grade 3-5 AE, as specified in the primary endpoint definition (Section 4.1).

A by-subject listing of dosing of study medication (record of study medication, infusion details, and dose changes) and a listing of batch numbers will be also provided.

Table 7.4.1-1: Study Therapy Parameter Definitions for Arms A and B During Part 1 (Combination Portion)

	Nivolumab Arm A	Nivolumab Arm B	Ipilimumab Arm A	Ipilimumab Arm B
Dosing Schedule per Protocol	3 mg/kg every 3 weeks for 4 doses	1 mg/kg every 3 weeks for 4 doses	1 mg/kg every 3 weeks for 4 doses	3 mg/kg every 3 weeks for 4 doses
Dose	Dose (mg/kg) is defined as the minimum of [vial strength (mg/mL) *total volume infused (mL)] /most recent weight (kg) and nominal dose (mg/kg) * total volume infused (mL) /total volume prepared (mL)	Dose (mg/kg) is defined as the minimum of [vial strength (mg/mL) *total volume infused (mL)] /most recent weight (kg) and nominal dose (mg/kg) * total volume infused (mL) /total volume prepared (mL)	Dose (mg/kg) is defined as the minimum of [vial strength (mg/mL) *total volume infused (mL)] /most recent weight (kg) and nominal dose (mg/kg) * total volume infused (mL) /total volume prepared (mL)	Dose (mg/kg) is defined as the minimum of [vial strength (mg/mL) *total volume infused (mL)] /most recent weight (kg) and nominal dose (mg/kg) * total volume infused (mL) /total volume prepared (mL)
Cumulative Dose	Cum Dose (mg/kg) is the sum of the doses administered to a subject during Part 1.	Cum Dose (mg/kg) is the sum of the doses administered to a subject during Part 1.	Cum Dose (mg/kg) is the sum of the doses administered to a subject during Part 1.	Cum Dose (mg/kg) is the sum of the doses administered to a subject during Part 1.
Relative Dose Intensity (%)	$\text{Cum dose} / [3 \times (\text{Last Part 1 dose date} - \text{Start dose date} + 21) / 21] \times 100$	$\text{Cum dose} / [1 \times (\text{Last Part 1 dose date} - \text{Start dose date} + 21) / 21] \times 100$	$\text{Cum dose} / [1 \times (\text{Last Part 1 dose date} - \text{Start dose date} + 21) / 21] \times 100$	$\text{Cum dose} / [3 \times (\text{Last Part 1 dose date} - \text{Start dose date} + 21) / 21] \times 100$
Infusion Duration (mins)	Each infusion duration is calculated as infusion stop date/time - infusion start date/time.	Each infusion duration is calculated as infusion stop date/time - infusion start date/time.	Each infusion duration is calculated as infusion stop date/time - infusion start date/time.	Each infusion duration is calculated as infusion stop date/time - infusion start date/time.
Duration of Treatment	Last Part 1 dose date - Start dose date +1	Last Part 1 dose date - Start dose date +1	Last Part 1 dose date - Start dose date +1	Last Part 1 dose date - Start dose date +1

Table 7.4.1-2: Study Therapy Parameter Definitions for Arms A and B During Part 2 (Maintenance)

Nivolumab Arms A and B	
Dosing Schedule per Protocol	480 mg flat dose every 4 weeks
Dose	Dose (mg) = total dose delivered as recorded on Record of Study Medication CRF
Cumulative Dose	Cum Dose (mg) is the sum of the doses administered to a subject during Part 2.
Relative Dose Intensity (%)	$[\text{Cumulative dose (mg)} / ((\text{Last dose date in Part 2} - \text{first dose date in Part 2} + 28) \times 480/28)] \times 100$
Infusion Duration (mins)	Each infusion duration is calculated as infusion stop date/time - infusion start date/time.
Duration of Treatment	last dose date in Part 2- first dose date in Part 2 + 1

Table 7.4.1-3: Study Therapy Parameter Definitions for Cohort C

	Nivolumab	Ipilimumab
Dosing Schedule per Protocol	6 mg/kg followed 4 weeks later by 480 mg flat dose repeated every 8 weeks	1 mg/kg every 8 weeks
Dose (mg/kg) for weight based dosing	Dose administered (mg)/Most recent weight (kg).	Dose administered (mg)/Most recent weight (kg).
Dose (mg) for flat dosing	total dose delivered as recorded on Record of Study Medication CRF	N/A
Cumulative Dose (mg/kg) for weight based dosing	the sum of the weight based doses administered to a subject	the sum of the weight based doses administered to a subject
Cumulative Dose (mg) for flat dosing	the sum of the flat doses administered to a subject	N/A
Relative Dose Intensity (%) for weight based dosing	$\text{Cum dose (mg/kg)} / [(\text{Last dose date} - \text{Start dose date} + 56) \times 6/56] \times 100$	$\text{Cum dose (mg/kg)} / [(\text{Last dose date} - \text{Start dose date} + 56) \times 1/56] \times 100$

Table 7.4.1-3: Study Therapy Parameter Definitions for Cohort C

	Nivolumab	Ipilimumab
Relative Dose Intensity (%) for flat dosing	$\left[\frac{\text{Cumulative dose (mg)}}{(\text{Last dose date} - \text{start dose date} + 56) \times 480/56} \right] \times 100$	N/A
Relative Dose Intensity (%)	$1/2 * [\text{Relative Dose Intensity (\%)} \text{ for weight based dosing} + \text{Relative Dose Intensity (\%)} \text{ for flat dosing}]$	Same as Relative Dose Intensity (%) for weight based dosing

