Both agents given as single agent is uncommonly associated with infusion reactions, incidence less than 1% for ipilimumab (Yervoy® FDA Label) and for nivolumab 3%.⁹ In the CA209069 study, hypersensitivity/infusion reactions were listed as 3.2% for the combination and 2.2% for ipilimumab. No Grade 3 or Grade 4 hypersensitivity/infusion reactions were observed in either the combination or single agent ipilimumab treatment groups.²⁵

Subjects should be carefully monitored for infusion reactions during nivolumab/ipilimumab administration. If an acute infusion reaction is noted, subjects should be managed according to [Section 4.4](#).

The **pharmacy manual** includes detailed instructions for study medication preparation.

Dosing calculations should be based on the body weight assessed at screening. It is not necessary to re-calculate subsequent doses if the subject weight is within 10% of the weight used to calculate the previous dose. All doses should be rounded to the nearest milligram.

During Part 1, subjects may be dosed no less than 19 days between doses. If dosing is delayed, both nivolumab and ipilimumab must be delayed together. If dosing is resumed after a delay, both nivolumab and ipilimumab must be resumed on the same day.

Detailed instructions for dilution and infusion of nivolumab/ipilimumab injection may be provided in the pharmacy binder, pharmacy reference sheet or current investigator brochure.^{23,26} Care must

be taken to assure sterility of the prepared solution as the product does not contain any antimicrobial preservative or bacteriostatic agent.

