6.2 Treatment Regimens

Arms A and B:

The treatment group **“as randomized”** will be retrieved from the IVRS system:

- Arm A (N3I1): Experimental arm: nivolumab 3 mg/kg + ipilimumab 1 mg/kg administered every 3 weeks for 4 doses followed by nivolumab flat dose 480 mg every 4 weeks
- Arm B (N1I3): Control arm: nivolumab 1 mg/kg + ipilimumab 3 mg/kg administered every 3 weeks for 4 doses followed by nivolumab flat dose 480 mg every 4 weeks

The treatment group **“as treated”** will be the same as the **“as randomized”** as long as the subject received at least one dose of study medication.

Cohort C:

All subjects will be assigned nivolumab 6 mg/kg + ipilimumab 1 mg/kg administered every 8 weeks alternating with a flat dose of 480 mg nivolumab every 8 weeks. The treatment group **“as treated”** will be the same as the assigned treatment as long as the subject received at least one dose of study medication.

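### The Part 1 exposure summaries for Arms A and B cap each dose at nominal and so cannot show per-infusion overdosing, and no planned table groups subjects by the regimen they received

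*SAP*

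**What the plan says.** SAP 7.4.1, Table 7.4.1-1, gives the same dose rule for both drugs in both arms during Part 1. It starts "Dose (mg/kg) is defined as the minimum of" and compares two quantities. The first is vial strength times volume infused, divided by the most recent weight. The second is "nominal dose (mg/kg) * total volume infused (mL) /total volume prepared (mL"). Cumulative dose is the sum of these doses. RDI divides that sum by the planned dose (3 or 1 mg/kg, by arm and drug) times (last dose date − first dose date + 21)/21.

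SAP 7.4.1 tabulates "Relative dose intensity (%) using the following categories", the highest being 110% or more. It repeats the Part 1 summary for subjects who had the drug-related Grade 3-5 event that defines the primary endpoint.

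On grouping, SAP 6.2 states: "The treatment group “as treated” will be the same as the “as randomized” as long as the subject received at least one dose". SAP 7.4 adds: "Analyses will be performed by treatment group “as treated” in all treated subjects, unless otherwise specified".

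The other two exposure tables have no cap. Part 2 (Table 7.4.1-2) uses the dose delivered as recorded on the CRF, and weight-based dosing in Cohort C (Table 7.4.1-3) uses mg administered divided by weight.

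Protocol 4.3.1 bases dosing on screening weight, sets a minimum of 19 days between Part 1 doses, and says: "It is not necessary to re-calculate subsequent doses if the subject weight is within 10% of the weight used to calculate the previous dose".

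**The concern.** Arms A and B use the same two drugs and differ only in the Part 1 doses, and the primary endpoint is severe drug-related toxicity. The Part 1 exposure tables, above all those restricted to subjects with the primary event, are where a reader would look to see whether excess drug accompanied an event. The dose rule is one-sided: a shortfall passes through to the summary, while an excess is cut back to nominal. An RDI category of 110% or more suggests that excess would be visible when it would not.

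The as-treated rule adds to this. Because any single dose fixes a subject in the randomized arm, a subject who received the other arm's regimen is counted under the randomized regimen in every safety and exposure table.

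**Working it through.** **Inputs.** Dose and RDI formulas: SAP Table 7.4.1-1. RDI categories: SAP 7.4.1. Minimum interval of 19 days and 10% weight tolerance: Protocol 4.3.1. Vial strengths of 10 mg/mL (nivolumab) and 5 mg/mL (ipilimumab): Protocol Table 4-1. Sample size and rates: SAP 5. Assumptions: nominal means the assigned dose, as the RDI denominators of 3, 1, 1 and 3 imply, and infused volume does not exceed prepared volume.

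**1. The plan's own figure.** With 170 per arm, 40% vs 55% and two-sided alpha 0.05, power is 79.4% by the pooled normal approximation and 80.0% unpooled. The stated 80% is reproduced.

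**2. The cap.** Dose = min(strength × V_inf / weight, nominal × V_inf / V_prep). Since V_inf / V_prep ≤ 1, the second term is at most nominal, and so is the minimum.

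**3. Highest RDI when every dose is at the cap.** For n doses at interval d, RDI = n × 21 / [(n − 1) × d + 21].
- d = 19: two doses 42/40 = 105.0%; three 63/59 = 106.8%; four 84/78 = 107.7%.
- d = 18, shorter than allowed: three doses 63/57 = 110.5%; four 84/75 = 112.0%.

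The top category is reached only through early dosing, never through excess drug in an infusion.

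**4. Arm A subject given ipilimumab 3 mg/kg in full.** The first term is at least 3 (more if volume includes diluent) and the second is 1 × 1 = 1. The recorded dose is 1 mg/kg, so the summary shows 100% against a true 300%. This holds whatever volume means.

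**5. The under-dosed half of a full swap.** Take an assumed weight of 80 kg and a complete infusion.
- Volume is undiluted drug: min(1, 3) = 1, RDI 1/3 = 33%, for nivolumab in a swapped Arm A subject and for ipilimumab in a swapped Arm B subject.
- Volume includes 20 mL diluent: nivolumab (8 + 20) × 10/80 = 3.5, cut to 3, RDI 100%; ipilimumab (16 + 20) × 5/80 = 2.25, RDI 75%.
- Volume includes 50 mL diluent: nivolumab (8 + 50) × 10/80 = 7.25 and ipilimumab (16 + 50) × 5/80 = 4.1, both cut to 3, RDI 100%.

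The SAP does not say which volume is meant.

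**6. Weight change at the 10% limit, dose not recalculated.** After a loss the true dose is 1/0.9 = 111% of nominal and is recorded as 100%. After a gain the true dose is 1/1.1 = 91% and is recorded as 91% if volume means undiluted drug.

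**7. Effect of swaps on the primary test.** If a share s of each arm is swapped and analysed as randomized, the difference is 15 × (1 − 2s) points. The shares are assumed, since the documents give none; power is by the pooled approximation.

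| Share swapped per arm | Difference (points) | Power |
|---|---|---|
| 0% | 15.0 | 79.4% |
| 1% | 14.7 | 77.7% |
| 2% | 14.4 | 76.0% |
| 5% | 13.5 | 70.4% |
| 10% | 12.0 | 60.2% |

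**The case against.** A reader might infer that overdoses and arm swaps cannot appear anywhere in the trial's output. The documents do not support that.
- Protocol 6.6 requires every overdose to be reported as a serious adverse event. SAP 7.4.1 plans a by-subject dosing listing with infusion details. SAP 7.2.2 sends non-programmable and significant on-treatment deviations to listings. Protocol 4.6 provides an unblinded pharmacist and an unblinded monitor.
- The under-dosed half of a swap can show as 33%, in the lowest RDI category, if volume means undiluted drug.
- The top RDI category can be reached by dosing off schedule.
- The weight example is permitted dosing, not an overdose, and seldom changes a category. With dose 1 at screening weight and doses 2 to 4 at a full 10% loss, uncapped RDI at 21-day intervals is (1 + 3 × 1.111)/4 = 108.3%, in the same 90 to <110% band as the capped 100%.

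All of this stands and limits the reach of the point. It does not rescue the summaries. The other routes are individual reports and listings, and they depend on the error being noticed. Investigators and site staff are blinded in Part 1, so recognition rests largely on the unblinded staff. The programmable deviations in SAP 7.2.2 include no dosing-error or wrong-arm item. SAP 6.1.2.1 identifies Part 1 dosing by volume infused, whereas SAP 6.1.2.2 uses mg delivered for Part 2. That suggests, without proving, that the Part 1 record holds volumes from which an excess is not evident. The Core Safety SAP is not among the documents and may add something.

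A reader might also infer that the primary result is biased by the dose formula. It is not: SAP 7.6.1 counts subjects with an investigator-judged drug-related Grade 3-5 event and makes no use of derived dose.

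**Conclusion.** The point holds for the Part 1 summaries and for the grouping rule. Reading nominal as the assigned dose, the Part 1 cumulative-dose and RDI tables for Arms A and B cannot show per-infusion overdosing of any size: true values of 300% or 111% of nominal per dose are both summarised as 100%. RDI is bounded at 107.7% for subjects who keep the 19-day minimum interval. The cap does not apply to Part 2 or Cohort C. Separately, no planned table groups subjects by the regimen received.

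The consequence for the primary test is limited to the grouping rule. Symmetric undetected swaps shrink the difference and cannot create a false benefit; at assumed shares of 1% to 5% per arm, power falls to between 77.7% and 70.4%. How often overdoses or swaps occur is unknown from the documents, so the practical size cannot be stated. This is a correction that should be made to the SAP, not a flaw in the main test.

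**What to change.** 1. In Table 7.4.1-1, derive the Part 1 dose without a cap, as mg prepared (from the unblinded pharmacy record) × volume infused / volume prepared / weight. This brings it in line with Cohort C, where mg administered is divided by weight.
2. Define nominal dose, and state whether total volume includes diluent.
3. List every Part 1 dose above 110% of nominal.
4. In SAP 6.2, define as-treated by the Part 1 regimen actually received, and state how partial swaps (for example, one cycle or one drug) are classed. Use it for the safety and exposure tables and for one sensitivity analysis of the primary endpoint. Keep as-randomized for the main test.

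The cost is SAP wording, transfer of pharmacy preparation records at database lock (records that unblinded staff already oversee), and one extra analysis. Sample size and the main test do not change.

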7.4.2 Modifications of Study Therapy

7.4.2.1 Dose Delays

Each nivolumab and ipilimumab infusion may be delayed. A dose will be considered as actually delayed if the delay is exceeding 3 days (ie greater than or equal to 4 days from scheduled dosing date) for both nivolumab and ipilimumab. All studies drugs must be delayed until treatment can resume. Reason for dose delay will be retrieved from CRF dosing pages.

The following parameters will be summarized by treatment group:

- Number of dose delays per subject, length of delay, and reason for delay

7.4.2.2 Infusion interruptions and Rate Changes

Each nivolumab or ipilimumab infusion can be interrupted and/or the IV infusion rate can be reduced. This information will be retrieved from CRF dosing pages.

The following parameters will be summarized by treatment group:

- Number of subjects with at least one dose infusion interruption, the reason for interruption, and the number of infusion interruptions per subject.
- Number of subjects with at least one IV infusion rate reduction and the reason for reduction.

7.4.2.3 Dose Escalations

Dose escalations are not permitted for either nivolumab or ipilimumab.

7.4.2.4 Dose Reductions

Dose reductions are not permitted for either nivolumab or ipilimumab.

7.4.2.5 Dose Omissions

Dose omissions are not permitted for either nivolumab or ipilimumab.

7.4.3 Concomitant Medications

Concomitant medications, defined as medications other than study medications which are taken at any time on-treatment (ie, on or after the first day of study therapy and within 100 days following the last dose of study therapy), will be coded using the WHO Drug Dictionary.

The following summary table will be provided:

- Concomitant medications (subjects with any concomitant medication, subjects by medication class and generic term)

A by-subject listing will accompany the table.

